
• Geometric Mean Antibody Concentrations (GMCs) at Year 3, 4, 5, 6, 7, 8, 9 and 10;• Reverse Cumulative Distribution Plots (RCDPs) at Year 3, 4, 5, 6, 7, 8, 9 and 10;• Percentages of subjects with RVNA concentrations ≥ 0.5 IU/mL, as measured by RFFIT assay at Year 3, 4, 5, 6, 7, 8, 9 and 10.		

Name of Sponsor: GlaxoSmithKline Biologicals S.A.	Protocol number: V49_23E1	Generic name of study vaccine(s): Rabies, whole virus vaccine (inactivated)
Statistical Analyses:		
Time to first RVNA concentrations <0.5 IU/mL		
Kaplan-Meier estimate of the survival function, along with 95% CIs, will be computed and displayed per each vaccination regimen. The Cox regression model will be used to compare the 3 vaccine regimens every year.		
Geometric Mean Concentration (GMC) and Geometric Mean Ratio (GMR)		
RVNA GMCs will be based on the logarithmically transformed (base10) values.		
GMCs, with the associated 95% confidence intervals will be computed for each vaccine group (assigned from parent study) at Year 3, 4, 5, 6, 7, 8, 9 and 10 by taking the exponential of the corresponding log-transformed (least squares) means and 95% confidence intervals, from an ANOVA model with fixed factors for group and center. Group differences along with 95% CIs will also be computed. Subjects will be included in this analysis until they receive the booster dose and they will be excluded thereafter.		
For subjects receiving a booster dose, analysis of boostability will be conducted 7 days (and also approximately 6 to 9 months) after administration of the booster dose by providing GMRs and associated 95% CIs, considering the antibody value at the booster visit as baseline (denominator) and the antibody concentration at 7 days (and also approximately between 6 to 9 months) after booster as the numerator.		
Reverse Cumulative Distribution Plots at Year 3, 4, 5, 6, 7, 8, 9 and 10;		
Reverse cumulative distribution plots will be provided at Year 3, 4, 5, 6, 7, 8, 9 and 10 by vaccination regimen group.		
Percentages of subjects with RVNA concentrations ≥0.5 IU/mL		
As a form of supplementary information, also percentage of subjects with RVNA concentrations ≥ 0.5 IU/mL, as measured by RFFIT assay at Year 3, 4, 5, 6, 7, 8, 9 and 10 will be presented in a tabular fashion.		
Interim Analyses: In order to understand complete evolution of the antibody decay over time and the effect		

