8.1.2.3 Secondary Immunogenicity Endpoint(s) (Amended 25 February 2019)

- GMCs at Year 3, 4, 5, 6, 7, 8, 9 and 10;

- Reverse Cumulative Distribution Plots (RCDPs) at Year 3, 4, 5, 6, 7, 8, 9 and 10;
- Percentages of subjects with RVNA concentrations ≥ 0.5 IU/mL, as measured by RFFIT assay at Year 3, 4, 5, 6, 7, 8, 9 and 10.

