8.4.3.3.3 Statistical Methods

Geometric Mean Concentration (GMC).

RVNA GMCs will be based on the logarithmically transformed (base10) values.

GMCs with the associated 95% confidence intervals (CIs) will be computed for each vaccine group at Year 3, 4, 5, 6, 7, 8, 9 and 10 by taking the exponential of the corresponding log-transformed (least squares) means and 95% confidence intervals, from an ANOVA model with fixed factors for group and center. Group differences along with

95%CIs will also be computed. Subjects will be included in this analysis until they receive the booster dose and they will be excluded thereafter.

Reverse Cumulative Distribution Plots.

The reverse cumulative distribution plots will be provided at Year 3, 4, 5, 6, 7, 8, 9 and 10 by treatment group.

Percentages of subjects with RVNA concentrations ≥ 0.5 IU/mL.

As a form of supplementary information, also percentage of subjects with RVNA concentrations ≥ 0.5 IU/mL, as measured by RFFIT assay at Year 3, 4, 5, 6, 7, 8, 9 and 10 will be presented in a tabular fashion.

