8. GENERAL ISSUES FOR STATISTICAL ANALYSES

8.1. Adjustment for Covariates

Cox proportional hazards regression model – Time to first RVNA <0.5IU/mL

The hazard ratio (HR) from the Cox ([Andersen](#), 1982) proportional hazards regression model will be used as a treatment effect measure for time to event endpoints.

Group comparisons for first occurrences of a booster (i.e., RVNA concentration <0.5 IU/mL) will be performed using an adjusted Cox proportional hazard regression model with effect for treatment and center. Ties will be handled with the exact method as it assumes that there is a true but unknown ordering for the tied event times.

Analysis of Variance (ANOVA) – Analysis of boostability.

For subjects who will receive rabies vaccine booster the log-transformed antibody concentration at day 7 will be analyzed using an Analysis of Variance (ANOVA) which includes treatment (vaccine received at time of parent study V49_23) and center. Summary tables will show adjusted GMCs and GMR for each treatment and adjusted ratios of GMCs between vaccine groups.

Mixed model for repeated measures – Analysis of persistence

Log-transformed antibody titers as collected at annual Scheduled Visits (from Visit 1 to Visit 7) will be analyzed using a mixed model for repeated measures within subject, including time and treatment as independent variables, their interaction and a random intercept with an unstructured covariance matrix.

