8.7. Data Transformation

Distributions of antibodies are generally skewed to the right (Nauta, 2010). Therefore, antibody concentrations will be log10-transformed. GMCs and their 95% Confidence Intervals (CIs) are computed by exponentiating (base 10) the least squares means and 95% CIs of the log10 concentrations.

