8.8. Derived and Computed Variables

Data from parent study (V49_23)

Time to event analysis

For time to event analysis (i.e., Kaplan-Meier (KM) and Cox proportional hazard regression model), immunogenicity data from parent study, from day 57 up to one year, as well as data related to time between the end of parent study and start of this study (i.e., if subject receives a booster between the two studies) will be considered, as estimation of time to RVNA concentration drop below 0.5IU/mL.

Long term immunogenicity analysis

Demographics

Race and Age at time of V49_23 enrolment will be derived from demography of the parent study.

Body Mass Index (kg/m²) (BMI) will be calculated using the following formula: Weight (kg) / Height² (m²)

Time to Event

Survtime represents time to event/censoring in years:

Survtime variable will be derived using the planned visit day at which the event occurred or the subject is censored as time point.

The following SAS code describes how to derive **Survtime** from V49_23 study and from the current study (V49_23E1).

```

DATA <dbname>;
  SET <dbname>;
  IF LBORRES IN ('<0.1', '0.1', '0.2', '0.3', '0.4')
  THEN DROP ='Y';
  ELSE DROP ='N';
  format LABEL $12.;
  IF STUDYID = 'V49_23' THEN DO;
    IF VISITNUM = 9 THEN do;POINT =1; YEAR =57; LABEL = 'Day 57'; end;
    IF VISITNUM = 10 THEN do;POINT =2; YEAR =91; LABEL = 'Day 91'; end;
    IF VISITNUM = 11 THEN do;POINT =3; YEAR =181; LABEL = 'Day
181';end;
    IF VISITNUM = 12 THEN do;POINT =4; YEAR =365;LABEL = 'Day 366';end;
  END;
  IF STUDYID = 'V49_23E1' THEN DO;
    IF VISITNUM = 1 THEN do; YEAR = 3*365; LABEL = 'Year 3'; end;
    IF VISITNUM = 2 THEN do; YEAR = 4*365; LABEL = 'Year 4'; end;
    IF VISITNUM = 3 THEN do; YEAR = 5*365; LABEL = 'Year 5'; end;
    IF VISITNUM = 4 THEN do; YEAR = 6*365; LABEL = 'Year 6'; end;
    IF VISITNUM = 5 THEN do; YEAR = 7*365; LABEL = 'Year 7'; end;
    IF VISITNUM = 6 THEN do; YEAR = 8*365; LABEL = 'Year 8'; end;
    IF VISITNUM = 7 THEN do; YEAR = 9*365; LABEL = 'Year 9'; end;
    IF VISITNUM = 8 THEN do; YEAR = 10*365; LABEL = 'Year 10';end;
  END;
  Survtime= YEAR;

  IF DROP ='Y' THEN CENSOR=1; ELSE CENSOR = 0;
RUN;

```

Censor: represents censoring indicator variable: 0=censored, 1=event of interest;

Event of interest: RVNA concentration < 0.5 (censor=1)

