11.3. Secondary Objectives Analysis

Secondary Immunogenicity Objective:

To evaluate the long-term (up to approx.10 years) immunogenicity in subjects who received a primary series of accelerated or conventional rabies PrEP intramuscular (IM) regimen in the parent study V49_23.

Yearly Geometric Mean Concentrations up to Year 10

All subjects enrolled in this extension study, independently from booster administration, are planned to be followed until year 10 from the primary vaccination.

Log-transformed antibody titers as collected at annual Scheduled Clinic Visits (from Visit 1 to Visit 7) will be analyzed using a mixed model for repeated measures within subject, including time, center and treatment as independent variables, interaction for time and treatment, a random intercept with an unstructured covariance matrix.

SAS code will look like the following:

```
PROC MIXED DATA = model;
  class subject time treatment center;
  model log_Ab = time treatment time*treatment center/ CL s ;
  lsmeans time treatment time*treatment;
  random intercept / subject = usubjid type = UN;
RUN;
```

Reverse Cumulative Distribution Figure (RCDF) up to Year 10

The percentages of subjects with concentration greater than or equal to defined RVNA values (on log10 scale) will be presented as reverse cumulative distribution curve, having the individual RVNA concentration on the X-axis and the percentage of subject with equal to or greater than the value on the Y-axis by each study visit (i.e., Year)

Note: If subject receives a booster during the study, for the purpose of the secondary objective analysis on long-term persistence of immune responses the RVNA concentration after the booster will not be 'entered' as such, but half of quantification level from that moment will be used for all consecutive visits.

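### The SAP's yearly-GMC mixed model stops at Visit 7 (Year 9) although Year 10 is required, and its code requests neither LS-mean confidence limits nor the yearly group differences

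*SAP*

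**What the plan says.** **Visit range.** SAP 11.3, under the heading "Yearly Geometric Mean Concentrations up to Year 10", states: "Log-transformed antibody titers as collected at annual Scheduled Clinic Visits (from Visit 1 to Visit 7) will be analyzed using a mixed model". SAP 8.1 describes the same model for titers "as collected at annual Scheduled Visits (from Visit 1 to Visit 7"). The visit coding in SAP 8.8 contains "IF VISITNUM = 8 THEN do; YEAR = 10*365; LABEL = 'Year 10';end", and the line before it maps Visit 7 to Year 9.

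**Required output.** Protocol 8.1.2.3 lists "GMCs at Year 3, 4, 5, 6, 7, 8, 9 and 10" as a secondary endpoint. Protocol 8.4.3.3.3 says that GMCs with 95% CIs "will be computed for each vaccine group at Year 3, 4, 5, 6, 7, 8, 9 and 10". The protocol synopsis adds "Group differences along with 95% CIs will also be computed", and 8.4.3.3.3 has the same requirement. SAP 8.7 obtains GMCs and their CIs by "exponentiating (base 10) the least squares means and 95% CIs of the log10 concentrations".

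**Code.** The PROC MIXED code in SAP 11.3 is introduced as indicative. It has no visit filter. The options `CL` and `S` are on the MODEL statement. The LSMEANS statement names time, treatment and their interaction, with no options. There is no ESTIMATE statement. The within-subject structure is a random intercept with `TYPE=UN`.

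**The concern.** Year 10 is the final time point of a persistence study planned to run to about 10 years. If the prose is followed, the arm GMCs and group comparisons at that point have no model in the SAP. A programmer who follows the prose and one who follows the heading would produce different tables. The earlier years can differ too, because both fits share variance components and center effects across visits. SAP 11.4 evaluates booster persistence by analogy with this analysis. If the visit limit carries over, a subject boosted at Ad hoc Visit 7.1 loses the only annual post-booster value, which is at Visit 8.

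The second gap would survive a correction of the digit. The protocol requires group differences with CIs at each year. The code does not request them, and no SAP text on the persistence analysis does so either: SAP 8.1 names adjusted between-group ratios only for boostability.

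**Working it through.** The documents give no figure to reproduce here: SAP 5 states that no sample size or power calculation was made. The check is a mapping and a count, followed by an assumption-based look at the covariance structure.

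**1. Years covered**

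| | Years | Count |
|---|---|---|
| Required (protocol 8.1.2.3, 8.4.3.3.3) | 3, 4, 5, 6, 7, 8, 9, 10 | 8 |
| Modelled (SAP 8.1 and 11.3, coded by SAP 8.8) | 3, 4, 5, 6, 7, 8, 9 | 7 |
| Missing | 10 | 1 |

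**2. Cells lost, with 3 arms**

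- GMCs: required 3 × 8 = 24, modelled 3 × 7 = 21, missing 3.
- Within-year pairwise differences: 3 pairs × 8 = 24 required, 3 × 7 = 21 modelled, missing 3.

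**3. What the code prints**

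- LSMEANS without `CL` gives estimates and standard errors but no confidence limits. LS-mean CIs are requested for 0 of 24 GMCs.
- `CL` and `S` on MODEL act on the regression coefficients. With the last sorted level as reference, a treatment main-effect coefficient is the difference from the reference arm at the reference visit. At any other visit, the difference from the reference arm is the sum of two coefficients. The third pair, between the two non-reference arms, is never a single coefficient.
- So exactly 2 within-year differences appear with a CI: 2 of 21 if Visits 1 to 7 are fitted, 2 of 24 if Visits 1 to 8 are. Another sort order changes which visit is the reference, not the count.
- `DIFF` on the 24 time-by-treatment cells would print 24 × 23 / 2 = 276 pairs, of which 24 are within-year.

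**4. Covariance (lesser point)**

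A single random intercept has a 1 × 1 covariance matrix, so `TYPE=UN` adds nothing. The implied structure is compound symmetry: one variance at every visit and one covariance for every pair of visits. An unstructured matrix over 8 visits has 8 × 9 / 2 = 36 parameters.

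The documents do not give the variances, decay rates or boosted shares. The effect was therefore examined over 5 × 3 × 3 × 2 × 2 × 2 = 360 **assumed** scenarios:

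- conventional Year-3 GMC 0.8, 1.5, 2, 3 or 5 IU/mL
- accelerated-to-conventional ratio 0.5, 0.75 or 1
- between-subject SD 0.35, 0.45 or 0.6 log10
- residual SD 0.15 or 0.25 log10
- decay 0.03 or 0.05 log10 per year
- slope SD 0 or 0.03

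Arm sizes were the maximum invited numbers: 211 (Conv-R), 209 (Acc-R/JE) and 158 (Conv-R/JE, assumed to behave like Conv-R). Data were complete. After a first value below 0.5 IU/mL at Visits 1 to 7, all later visits were set to 0.1 IU/mL, as in SAP 8.8. Observed values had no floor. The model variance was the mean of the eight visit variances, and the model covariance was the mean of the off-diagonal terms.

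Coverage of a nominal 95% CI = 2Φ(1.96 × model SE / true SE) − 1. For example, an SE ratio of 1.36 gives 2Φ(2.67) − 1 = 99.2%, and 0.84 gives 2Φ(1.65) − 1, about 90%.

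| Acc-R/JE vs Conv-R | SE ratio | Coverage | Median |
|---|---|---|---|
| Year 3 difference | 0.96 to 1.46 | 94.1% to 99.6% | 98.2% |
| Year 10 difference | 0.84 to 1.36 | 89.9% to 99.2% | 93.9% |
| Year 3 to Year 10 change (not a protocol output) | 0.67 to 0.93 | 81.2% to 93.2% | 88.7% |

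If the below-0.5 value itself is also imputed (one reading of SAP 8.2.2), Year-10 coverage is 91.1% to 99.5% (median 94.8%). A floor at 0.1 IU/mL leaves Year 10 essentially unchanged. With an unstructured within-subject matrix, Year-10 coverage is 94.3% to 96.6%.

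**The case against.** **It is an obvious slip.** The heading, the follow-up sentence below it, the unfiltered code and the protocol all point to Year 10. This is probably right as to intent. But the limit stands in two operative sections, and neither the SAP's change history nor any other text gives a reason for it.

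**Year 10 does have a method.** Protocol 8.4.3.3.3 specifies a by-year ANOVA with group and center, giving CIs and group differences. That is true, but the SAP does not carry it over, and its data rule differs. The protocol drops subjects after a booster, whereas SAP 8.2 and 8.8 impute half the quantification level. Using the ANOVA for Year 10 alone would put that year on a different basis from Years 3 to 9. The plain GMC formula in SAP 8.8 gives no CI and no comparison.

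**The gaps come from opposite readings.** Year 10 is lost only if the prose binds, and the LS-mean CIs only if the code binds, since SAP 8.7 asks for them in words. This is fair, and the counts in steps 2 and 3 should not be added together. The missing `CL` alone would be a trivial gap in indicative code. The group differences differ: neither the SAP prose nor the code requests them for persistence. The table shells, which are held outside the SAP, may do so.

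**The covariance point is preference.** Text and code agree on a random intercept, every simulation input is assumed, and the typical Year-10 departure is small. This largely stands, and the point is therefore optional.

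**Conclusion.** The concern holds. As written, SAP 8.1 and 11.3 exclude Year 10 from the only model the SAP gives for yearly GMCs. That leaves 3 of 24 GMCs and 3 of 24 within-year differences without a model. The code, read alone, requests no LS-mean CIs and prints 2 of the within-year differences. These counts follow from the documents and from default PROC MIXED behaviour.

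The weight is modest and the point should be fixed. The analysis is secondary, with no hypothesis (protocol 8.4.3.3.1) and no success criterion (8.2.2.3), and the time-to-event analysis and reverse cumulative plots reach Year 10. The covariance structure can miscalibrate intervals, but by how much rests wholly on assumed inputs, and the conclusion does not depend on it.

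**What to change.** 1. In SAP 8.1 and 11.3, replace Visit 7 by Visit 8 as the end of the range, so that the model covers Years 3 to 10.
2. In the 11.3 code, write `LSMEANS time*treatment / CL DIFF`. State in the text that the 24 within-year pairwise differences are reported, back-transformed as 10^x to GMC ratios with 95% CIs.
3. Use one subject identifier: the CLASS statement and the RANDOM statement now name different variables.
4. Optional, in the same edit: replace the RANDOM line by `REPEATED time / SUBJECT=usubjid TYPE=UN`, with the random-intercept model as the stated fallback if the fit does not converge.

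Items 1 and 2 cost one digit in two places, two options on one line and one reporting sentence. No new data are needed, because the Visit 8 blood draw is already scheduled. Item 4 costs 36 covariance parameters and a risk of non-convergence, which the fallback covers.

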11.4. Other Analysis

Analysis on subjects who received more than one booster dose

A contingency table by vaccine groups (from parent trial) will be presented, counting the frequency and the percentage of subjects receiving no booster, one booster dose, two booster doses and three or more booster doses during the extension trial.

Immunogenicity values after the second booster dose will not be used for any analyses. Subjects are kept in the study to monitor whether there is need for additional doses of vaccine in case RVNA concentrations go below 0.5IU/mL.

Analysis of booster persistence

Analogously to the long-term immunogenicity analysis, an evaluation of booster persistence will be performed using annual visit values after booster doses.

12. EFFICACY ANALYSIS

12.1. Primary Objectives Analysis

Not Applicable.

12.2. Secondary Objectives Analysis

Not Applicable.

12.3. Other Objectives Analysis

Not Applicable.

13. SAFETY ANALYSIS

The analysis of safety assessments in this study will include summaries of the following categories of safety data collected for subjects who will receive a rabies vaccine booster dose:

- Booster exposure.
- Unsolicited serious adverse events.

13.1. Analysis of Extent of Exposure

In this study only SAEs and the associated concomitant medications will be collected and only for those subjects who will be exposed to a rabies vaccine booster dose.

The period of observation for SAEs extends from the time the subject receives the booster dose until he or she completes the specified safety follow-up period (i.e the day of the next Scheduled Clinic Visit after booster vaccination or on the date of Early Termination Visit, whichever is earlier).

13.1.1. Safety Completeness Analysis

Not Applicable

13.2. Solicited Local and Systemic Adverse Events

Not Applicable

13.3. Unsolicited Adverse Events

This analysis applies only to SAEs occurring during the study and from the time of booster injection till the next Scheduled Clinic Visit (approximately 6 months after booster administration), judged either as probably related, possibly related, or not related to vaccination by the investigator, recorded in AE electronic Case Report Form (eCRF), with a start date on or after the date of booster dose. SAE starting prior to booster dose will not be recorded in the eCRFs.

The original verbatim terms used by investigators to identify SAEs in the CRFs will be mapped to PTs using the MedDRA dictionary. The SAEs will then be grouped by MedDRA PTs into frequency tables according to system organ class. SAEs judged by the investigator as at least possibly related to study vaccine will be summarized by vaccine group, according to system organ class and PT within system organ class. When an unsolicited SAE occurs more than once for a subject, the maximal severity and strongest relationship to the vaccine group will be counted.

Separate summaries will be produced for the following categories:

- Serious adverse events.
- Serious adverse events that are possibly or probably related to booster vaccination.
- Serious adverse event leading to withdrawal.
- Deaths

Data listings of all SAEs will be provided by subject. In addition, SAEs in the categories above will be provided as listed data. Only vaccine-emergent SAEs (see section 8.8 for definition) will be analyzed, i.e., excluding those eventually occurring after a subject has given informed consent but before booster vaccination.

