7.1.4 Serious Adverse Events

A serious adverse event (SAE) is defined as any untoward medical occurrence that at any dose results in one or more of the following:

- Death.
- Is life-threatening (i.e., the subject was, in the opinion of the investigator, at immediate risk of death from the event as it occurred); it does not refer to an event which hypothetically might have caused death if it were more severe.
- Required or prolonged hospitalization.
- Persistent or significant disability/incapacity (i.e., the event causes a substantial disruption of a person's ability to conduct normal life functions).
- Congenital anomaly/or birth defect.
- An important and significant medical event that may not be immediately life threatening or resulting in death or hospitalization but, based upon appropriate medical judgment, may jeopardize the subject or may require intervention to prevent one of the other outcomes listed above.

Adverse events which do not fall into these categories are defined as non-serious.

It should be noted that a serious adverse event need not, by definition, be severe.

In this study only SAEs and the associated concomitant medications following PCEC rabies booster vaccinations will be collected (see section 7.1.5, Methods for Recording Adverse Events and Serious Adverse Events).

The period of observation for SAEs extends from the time the subject receives the booster dose until completion of safety follow-up period (the day of the next Scheduled Clinic Visit after booster vaccination or on the date of Early Termination Visit, whichever is earlier).

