8.4.2 Analysis of Primary Objective(s)

8.4.2.1 Analysis of Primary Safety Objective

Number and percentages of SAEs will be summarized only for subjects receiving a booster dose by the vaccination regimen received in the parent study V49_23 and overall.

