
Clarification of the timeframe between each yearly Scheduled Visit: Visit 1 date has to be used as reference for calculating next visit date (e.g. Visit 1: 31 JAN 15, then Visit 2: 31 JAN 16 ± 28 days, Visit 3: 31 JAN 17 ± 28 days) (Table 2a).Clarification of the time window between the Scheduled Clinic Visit and the Ad hoc Visit: the previous wording was not clear enough, team agreed to precise that booster administration at the Ad hoc Visit should happen between 6 to 9 months after the Scheduled Clinic Visit (Table 2b).Clarification that physical exams have to be done by practitioners in accordance with their institutional policy (Table 2a and 2b, Section 5.1.2 Screening). It has been specified that collection of vital signs must be done during all Ad hoc Visits prior booster administration. During the other visits (Scheduled and Additional), they could be measured at the discretion of the investigator (Section 5.1.2 Screening).Clarification on the number of additional booster doses a subject may receive: if, after a first booster dose, the adequate RVNA level is not reached at two consecutive determinations, a subject may receive an additional booster. If he/she is still a non-responder, the investigator should manage at its discretion. (Synopsis; Section 3.1 Overview of Study Design; Section 5.2 Ad hoc Clinic Visits; Section 6.3 Vaccine Preparation and Administration).Clarification on premature withdrawal from the study: there was no mention on the	

procedure to follow in case a subject misses the Ad hoc Visit and the possible booster dose. This has been added to the relevant section, specifying that in this case the subject could come to the next following Scheduled Visit and having a blood draw according to protocol. In case RVNA concentrations <0.5 IU/mL, a booster may be given. (*Section 3.8 Premature Withdrawal from Study*).

- Clarification on Exclusion Criteria: prior to Scheduled Visit criteria have been added, as they were not previously detailed (only criteria prior to study entry and booster vaccination were stated).

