11.2. Primary Objectives Analysis

Primary Immunogenicity Objectives:

1. To compare the long-term (up to approx.10 years) persistence of antibody responses (i.e. time until antibody concentrations drop below 0.5 IU/mL) in subjects who received a primary series of accelerated or conventional rabies PrEP intramuscular (IM) regimen in the parent study V49_23.
2. To evaluate the antibody responses to a booster dose of Purified Chick Embryo Cell-Culture (PCEC) rabies vaccine administered to subjects with Rabies Virus Neutralizing Antibody (RVNA) concentrations < 0.5 IU/mL following a primary series of accelerated or conventional rabies PrEP IM regimen in the parent study V49_23.

Primary hypotheses:

There is no null hypothesis associated to primary objectives.

Time to first RVNA concentrations < 0.5 IU/mL

Cox proportional hazards regression model

Since, already at the end of the parent study (Day 366, study V49_23) it was observed a difference in the persistence of adequate RVNA concentrations between subjects who have received the accelerated PrEP schedule and those who received the conventional rabies vaccines schedule, the HR from the Cox proportional hazards regression model will be used as a treatment effect measure for time to event endpoints.

Statistical model:

An adjusted proportional hazards regression Cox model will be used:

$$h(t) = h_0(t) \cdot \exp(\beta_1 x_1 + \beta_2 x_2)$$

where:

t represents the survival time

$h(t)$ is the hazard function as determined by the covariates treatment and center

$h_0(t)$ is the baseline hazard function at time t

X_1 represents treatment

X_2 represents center

β_1 and β_2 are the unknown parameters for treatment and center, to be estimated.

The HR is a multiplicative constant $\exp(\beta_1)$ comparing the hazard function in the accelerated schedule group relative to the hazard function in the conventional schedule group.

The HR will be derived from the Cox proportional hazards model using SAS PROC PHREG (with TIES=EXACT).

HR point estimate(s) will be based on partial maximum likelihood function, and Wald-test based two-sided 95% confidence intervals will be requested by the RISKLIMITS option.

The following SAS code will be applied:

```
PROC PHREG data=<dataset>;
  class arm center;
  MODEL survtime*status(0)=ARM center/ TIES=EXACT RISKLIMITS;
  RUN;
```

survtime represents variable containing event/censoring times.

status represents censoring variable (0=censored, 1=event).

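### The primary safety percentages rest on a post-booster window of varying length that the SAP calls about six months; SAE percentages by regimen may not be comparable if booster timing differs

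*SAP*

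**What the plan says.** Protocol 8.4.2.1 defines the primary safety summary, which is also to be given for all regimens together: "Number and percentages of SAEs will be summarized only for subjects receiving a booster dose by the vaccination regimen received in the parent study V49_23". Protocol 8.4.2.1.3 and SAP 13.3 add tables by system organ class and preferred term.

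Protocol 7.1.4 opens the window at the booster: "The period of observation for SAEs extends from the time the subject receives the booster dose until completion of safety follow-up period". Its closing date is then given as "the day of the next Scheduled Clinic Visit after booster vaccination or on the date of Early Termination Visit, whichever is earlier". SAP 13.1 repeats this. SAP 13.3 gives the window a length, describing it as running "from the time of booster injection till the next Scheduled Clinic Visit (approximately 6 months after booster administration", and Table 4 in SAP 7.7 labels the safety period in the same way.

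The dates that determine the window appear in several places:

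- Scheduled visits fall on the Visit 1 anniversary, plus or minus 28 days (Protocol Table 2a).
- The booster falls 6 to 9 months after the preceding Scheduled Clinic Visit (Protocol Synopsis, Table 2b and 5.2; header of SAP Table 3). The Amendment 2 rationale says "booster administration at the Ad hoc Visit should happen between 6 to 9 months after the Scheduled Clinic Visit".
- Footnote a of SAP Table 3 still puts the booster at about 6 months.
- The later post-booster measurement is placed 6 to 9 months after the booster in the Synopsis (Statistical Analyses) and SAP 8.8, but at about 6 months in Protocol 8.4.2.3.3 and SAP 11.2.

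No analysis accounts for post-booster follow-up. Protocol 8.4.2.1.1 (extent of exposure) and SAP 13.1.1 (safety completeness) are marked not applicable. SAP 9.1 summarises time under observation, but the only study duration defined in SAP 8.8 starts at Visit 1, not at the booster.

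**The concern.** The window closes on a calendar date that does not move with the booster. The later the booster falls after the qualifying blood draw, the shorter the time in which an SAE can be counted. A crude percentage treats a subject watched for three months like one watched for six.

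Safety of the booster is a primary objective, and its result is tabulated by regimen. Low antibody triggers the booster, and SAP 11.2 reports that at Day 366 of the parent study "it was observed a difference in the persistence of adequate RVNA concentrations between subjects who have received the accelerated PrEP schedule" and those on the conventional one. Regimens may therefore be boosted in different years and, if practice shifted over time, at different intervals. The Year 6 interim report, which may go to a health authority, and the final report could likewise cover different mixes of window length. A reader of either could not tell how long boosted subjects were followed.

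**Working it through.** **Inputs from the documents.** Visits are one year apart, plus or minus 28 days. The booster is at 6 to 9 months. SAE collection ends at the next Scheduled Clinic Visit. I use a 365-day year and months of 365/12 days.

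**Step 1: the SAP's own figure.** With the booster at 6 months, the window is 12 − 6 = 6 months, or 182.5 days. This reproduces the SAP's statement, but only for a booster at 6 months.

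**Step 2: the window at 6 to 9 months.** Window = 365 + (shift in visit dates) − booster month × 365/12.

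| Case | Shortest (booster at 9 months) | Longest (booster at 6 months) | Ratio |
|---|---|---|---|
| Visits on time | 91 days | 182 days | 2.0 |
| Booster after Visit 1 (closing visit ±28) | 63 days | 210 days | 3.3 |
| Booster after Visits 2 to 7 (both visits ±28) | 35 days | 238 days | 6.8 |

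The nominal midpoint is 12 − 7.5 = 4.5 months (137 days). Six months is the upper end of the nominal range.

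**Step 3: the conflicting passages.** If the next scheduled sample is instead 6 to 9 months after the booster (Synopsis, SAP 8.8), the nominal window is 6 to 9 months and the booster falls 12 − 9 = 3 to 12 − 6 = 6 months after the preceding visit. Six months is then the lower end. On either reading it is an endpoint of the range and not its centre.

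**Step 4: effect on a percentage.** The documents give no SAE rate, so I assume a constant 1%, 2% or 5% of subjects per year. Expected percentage = 1 − exp(−rate × window/365).

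| Window | 1% per year | 2% per year | 5% per year |
|---|---|---|---|
| 35 days | 0.10% | 0.19% | 0.48% |
| 91 days | 0.25% | 0.50% | 1.24% |
| 137 days | 0.37% | 0.75% | 1.86% |
| 182 days | 0.50% | 1.00% | 2.47% |
| 238 days | 0.65% | 1.30% | 3.21% |

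**Step 5: effect on regimens with the same true rate.** Booster dates by regimen are not given. As an illustration, let a share *a* of one regimen's boosters have a 6-month window and the rest a 4.5-month window, with share *c* in the other regimen. Mean window = share × 182.5 + (1 − share) × 136.9 days. For 80% v 20% this is 173 v 146 days, a ratio of 1.19.

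| Shares *a* v *c* | Ratio of mean windows | At 2% per year | At 5% per year |
|---|---|---|---|
| 50% v 50% | 1.00 | 0.87% v 0.87% | 2.16% v 2.16% |
| 60% v 40% | 1.06 | 0.90% v 0.85% | 2.22% v 2.10% |
| 80% v 20% | 1.19 | 0.95% v 0.80% | 2.35% v 1.98% |
| 100% v 0% | 1.33 | 1.00% v 0.75% | 2.47% v 1.86% |

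Swapping the shares reverses the direction. If one regimen were boosted entirely at 6 months and the other entirely at 9, the contrast would be two-fold (1.00% v 0.50% at 2% per year).

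**The case against.** A reader might infer that the design makes SAE percentages differ by regimen as a matter of course. It does not. One rule covers all three regimens, and the ratio is 1.00 when booster timing is the same. SAP 11.2 gives neither the size nor the direction of the Day 366 difference, and the splits above are assumptions.

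A reader might also infer that windows became shorter after Amendment 2, so that the overall percentage understates risk. The amendment calls its timing change a clarification, no actual booster dates are given, and the passages in Step 3 point to longer windows. Nor do the documents say that missing the closing visit keeps a subject under collection for another year; they leave that case open.

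Further points stand against giving this much weight:

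- The 35- and 238-day extremes need both adjacent visits at opposite ends of their tolerance.
- There is no safety hypothesis, success criterion or planned test between regimens, so no inference is biased.
- At 5% per year the 80/20 gap is 0.37 points. Even if all 209 invited accelerated-regimen subjects were boosted, that is 0.0037 × 209, or about 0.8 of a subject.
- Every boosted subject is due an SAE assessment about 7 days after the booster. SAEs judged related must be reported whatever their timing (Protocol 7.1.5), and all SAEs are listed by subject.
- A person-time rate is not free of window length either. If risk is concentrated soon after the booster, the rate falls as the window lengthens.

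These points limit the size of the problem. They do not supply the missing follow-up summary or reconcile the stated length with the schedule.

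**Conclusion.** The point holds in a conditional form. The primary safety percentage ignores follow-up that is nominally 3 to 6 months under the 6-to-9-month booster timing and can reach 35 to 238 days within the visit tolerances. The SAP's figure of about six months matches only one end of that range, and other passages imply a different range. Percentages by regimen, or between the interim and final reports, may not be comparable if booster timing differs between them.

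The likely size is small: ratios of about 1.06 to 1.33 under the assumed splits, which is tenths of a percentage point at 2% to 5% per year and less at 1%. This rests on a constant SAE rate and on assumed rates and booster timing. It is a worthwhile low-cost improvement to the reporting of a primary objective, not a flaw that invalidates the safety analysis.

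**What to change.** In SAP 13.1 and 13.3 and Protocol 8.4.2.1, keep the count and percentage and add, by regimen and overall:

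1. The distribution of post-booster follow-up time, from the booster date to the closing visit or early termination.
2. The SAE rate per person-time observed over that interval, with an exact Poisson 95% CI. State whether the numerator is events or subjects with an event, and restrict it to the same interval, because the emergent-event definition in SAP 8.8 has a start but no end.
3. The percentage with an SAE in one fixed post-booster window that nearly all boosted subjects complete. This also covers the case in which risk is concentrated early.

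Replace the six-month description of the safety window in SAP 13.3 and Table 4 with the follow-up actually observed. Reconcile the timing statements in the Protocol Synopsis, Table 2b, 5.2 and 8.4.2.3.3 with those in SAP Table 3 (header and footnote a), Table 4, 8.8, 11.2 and 13.3. Which booster timing applies is for the sponsor to settle.

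Booster and visit dates are already recorded, so no visit or procedure changes. The cost is SAP and protocol wording and one extra table, whose rates will be imprecise because few SAEs are expected.
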